#### PRIMARY AND SECONDARY VARIABLES

The primary objective will be to compare functional outcomes (Constant scale score)  
24 months after surgery in patients over 65 years of age with cuff arthropathies  
treated with either of the two options: medialized ITHA or lateralized ITHA, then the  
results obtained on the Constant scale at 24 m will be the variable of choice.

Constant scale at 24 m will be the primary variable. Secondary variables will include:  
visual analogue pain scale (VAS) and Quick-DASH and ASES questionnaires for  
functionality, range of motion, strength.

#### Statistical analysis

A descriptive analysis of the variables under study will be performed. The description of quantitative variables such as age, Charlson comorbidity index, questionnaires for the assessment of functionality (Constant, Quick-DASH, ASES), VAS and RHB sessions, will be carried out using the mean and standard deviation.

Categorical variables such as affected and dominant limb or satisfaction will be described by frequency and percentage. The normality of the available data will be checked using the Kolmogorov-Smirnov test.

To determine that both groups are similar, the Student's t-test will be used for continuous variables such as age, Charlson index and RHB sessions, while for categorical variables (dominant and affected limb and sex) the Pearson's chi-square test or Fisher's exact test will be used, depending on the characteristics of the variables.

Once the characteristics of the groups have been described, comparisons will be made between the two interventions (medialized IHTA and lateralized IHTA) in the main study variables. To determine whether there are statistically significant differences in

Prospective randomized clinical study to analyze the functional, radiological and strength results in lateralized and medialized models of reverse shoulder arthroplasty. Shoulder and Elbow Unit  
the Constant scale at 24 months between the two procedures, a general linear model will be performed. The same analysis will be used with the quick-DASH and ASES questionnaire.

For the analysis of strength during movement, VAS, as well as the rest of the questionnaires (including the standardized or age- and sex-adjusted Constant and the subsections of this questionnaire) at the different evaluation times of the study (1, 3, 6, 12, 18 and 24 months), the Student's t-test will be used. To compare the complications that occurred in both groups, Pearson's Chi-squared test will be used. Similarly, Pearson's Chi-square test will be used to compare satisfaction with what happened in each group.

Finally, to establish the existence of a relationship between Constant and normalized Constant and patient satisfaction, Pearson's correlation will be used. The results of the statistical tests will be given with a confidence level of 95%; that is, statistical significance will be set at 0.05. The statistical study will be performed using the IBM SPSS program (v.25).

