#### OBJECTIVE

The objective of this study is to determine the functional results (range of motion) and strength as well as the percentage of complications that appear with the use of two inverted arthroplasty systems (one medialized and the other lateralized).

In the treatment of rotator cuff arthropathies or irreparable cuff tears.

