Three weeks after surgery, new X-rays will be taken in three planes and referral to the Rehabilitation Center to begin active mobility, strengthening and gaining joint balance.

Visits 4, 5, 6 and 7: Groups 1 and 2. Three, Six, Twelve and 24 months after surgery.

Radiographic evaluation at each visit including the same three projections.

Clinical evaluation by means of the above mentioned scales and measurement of the BA to assess the functionality of the shoulder.

Finally in this phase, at the end of the follow-up of both groups (24 months), a cost analysis is performed by measuring direct costs (hospital stay, operating room costs, imaging tests, outpatient consultations, physiotherapy sessions, emergency visits, transport, medication consumption, etc.), medication consumption...) and indirect costs (need for home help, family leave...) and an isokinetic study of the shoulder (strength and mobility).

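### Strength is compared by an unadjusted t-test although sex and age are recorded: a valid test, but one that may give up precision and leaves a chance sex imbalance uncorrected

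*Combined protocol and SAP*

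**What the plan says.** All references are to the combined protocol and SAP.

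- **Status of strength.** The Objective section aims to "determine the functional results (range of motion) and strength as well as the percentage of complications". The section on primary and secondary variables makes the Constant score at 24 months primary and ends its list of secondary variables with "functionality, range of motion, strength".
- **Analysis of strength.** The Statistical analysis section groups it with pain and the remaining scores: "For the analysis of strength during movement, VAS, as well as the rest of the questionnaires (including the standardized or age- and sex-adjusted Constant". The sentence closes with the visits and the method: "1, 3, 6, 12, 18 and 24 months), the Student's t-test will be used". No covariate is named.
- **Use of sex and age.** Both appear only in the comparison of group characteristics, among the "continuous variables such as age, Charlson index and RHB sessions" and the "categorical variables (dominant and affected limb and sex".
- **Other models.** A general linear model is planned for the Constant at 24 months and for Quick-DASH and ASES. Its covariates are not listed, and it is not extended to strength.
- **Randomisation.** The Methodology section describes a random sequence and sealed envelopes, with no stratification.
- **Measurement.** The Procedure section places the "isokinetic study of the shoulder (strength and mobility" at the end of follow-up only. The schedule table lists strength in an assessment row that appears to be marked before the intervention, although the column alignment cannot be read with certainty.

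**The concern.** Men and women over 65 are eligible, with no upper age limit. If strength differs by sex or age, an unadjusted comparison leaves that variation in the error term. With about 17 to 21 patients per arm and no stratification, the arms may also end up with different proportions of men, and part of the observed strength difference would then reflect that mix. A significance test on baseline sex does not remove such a difference, and it has little power to detect one at this size.

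The plan already reports an age- and sex-adjusted Constant in the same sentence, so leaving strength unadjusted sits oddly beside it. At stake is how precisely the trial can answer one of its stated questions, and whether a decision to adjust might be taken only after an imbalance has been seen.

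**Working it through.** **1. The plan's own figures.** None is given for strength. The sample size concerns a 10-point Constant difference: 17 per group, raised to 21 per group for 20% losses. No SD is stated, so the 17 cannot be re-derived. It serves here only as the number expected at 24 months: 42 × 0.8 = 33.6, about 17 per arm.

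**2. Assumptions (not in the documents).** Proportion of men p = 20-50%. Men stronger than women by g within-sex SDs, with g from 0 to 2. True arm effect 1 within-sex SD. Age unrelated to strength within this over-65 population, which is unfavourable to the adjusted model. Two-sided 5% test.

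**3. Variance explained by sex.** R² = p(1−p)g² / (1 + p(1−p)g²).

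- g = 0.5: from 0.04/1.04 = 4% (p = 20%) to 0.0625/1.0625 = 6% (p = 50%)
- g = 1: from 0.16/1.16 = 14% to 0.25/1.25 = 20%
- g = 2: from 0.64/1.64 = 39% to 1/2 = 50%

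**4. Break-even.** Two covariates multiply the variance of the arm difference by about (1−R²) × (1 + 2/(N−5)). With N = 34 the second factor is 1 + 2/29 = 1.069, so the variances are equal at R² = 1 − 1/1.069 = 6.5%. Allowing also for 30 rather than 32 residual degrees of freedom, power is equal at R² of about 7%.

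**5. Simulated power, 17 per arm, across 20-50% men.**

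| Sex gap (within-sex SD) | t-test | Model with sex and age |
|---|---|---|
| 0 | 80-81% | 78-79% |
| 0.5 | 78-80% | 77-79% |
| 1 | 72-76% | 78-79% |
| 2 | 52-59% | 77-78% |

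A repeat run agreed to within about one percentage point. With no arm effect, both methods rejected in about 5% of trials.

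**6. Chance imbalance.** The SD of the difference in proportion of men is √(2p(1−p)/n). With n = 21 it is √(0.32/21) = 12.3 points at 20% men and √(0.5/21) = 15.4 points at 50%. With n = 17 the range is 13.7 to 17.1 points. At 30% men and n = 17, a gap of 20 points or more arises in 19% of randomisations.

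**7. Consequence of a given imbalance.** Take g = 1, 30% men, 17 per arm; the total SD is √1.21 = 1.1. A split of 14 vs 10 women shifts the unadjusted difference by (4/17)/1.1 = 0.21 total SD, and the t-test then rejects a true null about 7% of the time. A 14 vs 9 split gives (5/17)/1.1 = 0.27 SD and about 9.5%. A balanced 12 vs 12 split gives about 3%. These rates average out to the nominal 5%.

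**The case against.** The planned test is legitimate. Randomisation makes the unadjusted comparison unbiased on average and holds its level, and strength is a secondary outcome that did not drive the sample size. A reader might infer that the plan invites false positives caused by which arm has more men. The documents do not support that: rejections from chance imbalance are already counted in the 5%. What stands is the conditional bias once a particular imbalance has occurred, and the loss of precision.

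A reader might also infer that the t-test certainly loses power. That cannot be shown either. The documents give no strength SD, sex gap, arm effect or sex mix. At a 0.5 SD gap adjustment brings no gain, and with no gap it costs about 2-3 points. Nor does naming an adjusted Constant amount to a statement that strength depends on sex and age; it only makes this plausible.

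Finally, it would be too strong to say that sex and age are the only covariates available. The isokinetic study has no described preoperative value, but the schedule table appears to include strength before the intervention, and the plan does not say whether the strength it analyses is the isokinetic measure. A matching preoperative value would be a natural covariate. This changes the content of the model and does not rescue the plain t-test.

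**Conclusion.** The point holds as a recommended improvement to a secondary analysis, not as an error that invalidates it. The plan records sex and age, uses them only for comparability checks, and compares strength without them in a small, unstratified trial.

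Under the assumptions stated, adjustment ranges from a cost of about 2-3 points of power (no sex gap), through a gain of a few points (1 SD gap), to a gain of some 20 points or more (2 SD gap). Break-even is near 7% of variance explained. The SD of the chance sex imbalance is 12-15 points with 21 per arm. The overall type I error is about 5% either way. The true position within these ranges cannot be settled from the documents.

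**What to change.** Before any outcome data are examined, amend the Statistical analysis section so that strength is analysed by a linear model with arm, sex and age. Add preoperative strength for any outcome where the same measure was taken before surgery. State which strength measure is meant at each visit, and treat the 24-month isokinetic result as having no preoperative counterpart unless one is scheduled. Report the adjusted arm difference with its 95% CI, and keep the Student's t-test as a sensitivity analysis.

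The cost is SAP wording and two degrees of freedom out of 32 with 17 per arm, or three with a preoperative value. No new data are needed for sex and age. The downside is the loss of about 2-3 points of power if sex and age turn out not to be prognostic.

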## PROCEDURE

Visit 1: Attention at the HCSC Shoulder and Elbow Surgery Unit.

After an appropriate medical evaluation and physical examination, and having been diagnosed with rotator cuff arthropathy with the relevant complementary tests, the physician will evaluate whether the patient meets the inclusion criteria to be part of the present study. If so, he/she will explain in detail what the study consists of, in addition to handing him/her the Information Sheet and the Informed Consent Form, which he/she will read. Informed Consent, which will be read carefully and attentively. Once understood, and in case of accepting and signing the consent, the patient will be part of the study.

After being included in the surgical waiting list, the patient will be randomized to one of the two study groups: Group 1 treatment by means of inverted arthroplasty with medialized COR; Group 2 treatment by means of inverted arthroplasty with lateralized COR. Subsequently, the patient will be given the aforementioned functional assessment scales and the joint range of motion (ROM) will be measured using a manual goniometer.

Visit 2: Group 1 and 2. Admission and immediate postoperative period.

The patient will be admitted to undergo reconstructive surgery of the arthropathy, by means of one of the two mentioned Inverted Arthroplasty implants. The implants used will be registered, always following the same surgical technique with the same protocol (position, anesthesia, antibiotic prophylaxis...) and by one of the three surgeons of the shoulder unit, being always at least two of them present.

Complications occurring during surgery or in the immediate postoperative period will be recorded. During admission, before hospital discharge, a hemogram will be obtained to assess the patient's anemization.

Prospective randomized clinical study to analyze the functional, radiological and strength results in lateralized and medialized models of reverse shoulder arthroplasty.

Shoulder and Elbow Unit

to evaluate the patient's anemization and a three-plane X-ray of the shoulder as the first post-surgical control. If required, all the tests necessary for an integral medical evaluation will be performed. After the operation, patients will be immobilized and will start passive exercises after 24/48 hours assisted by a physiotherapist.

Visit 3 : Group 1 and 2. Three weeks.

Three weeks after surgery, new X-rays will be taken in three planes and referral to the Rehabilitation Center to begin active mobility, strengthening and gaining joint balance.

Visits 4, 5, 6 and 7: Groups 1 and 2. Three, Six, Twelve and 24 months after surgery.

Radiographic evaluation at each visit including the same three projections.

Clinical evaluation by means of the above mentioned scales and measurement of the BA to assess the functionality of the shoulder.

Finally in this phase, at the end of the follow-up of both groups (24 months), a cost analysis is performed by measuring direct costs (hospital stay, operating room costs, imaging tests, outpatient consultations, physiotherapy sessions, emergency visits, transport, medication consumption, etc.), medication consumption...) and indirect costs (need for home help, family leave...) and an isokinetic study of the shoulder (strength and mobility).

## • PERIOD OF STUDY

PERIOD OF STUDY							
	Recruitment :	Randomization	Post-randomization				Closure
Starting point	-1	0	0w	1 W	1 M	6M	12 M
Recruitment:							
SelectionPatients		X					
Informed consent		X					
Randomization		X					
Interventions							
Lateralized RSA			X				
Medialized RSA			X				
AssessmentDemographic and epidemiological data, Constant, ASES, Quick Dash, VAS, RAM, Strength, Radiological		X					
			X				

Prospective randomized clinical study to analyze the functional, radiological and strength results in lateralized and medialized models of reverse shoulder arthroplasty.  
Shoulder and Elbow Unit

Adverse events		x	x	x	x	x	x	x
----------------	--	---	---	---	---	---	---	---

Study protocol. Diagram according to recommendations for intervention studies (SPIRIT).

#### ETHICAL ASSURANCE. RISKS AND BENEFITS.

The surgical procedure, follow-up and treatment of the patients operated by inverted arthroplasty with any of the two implants will be done in the same way as it is currently done in patients treated with these prosthetic systems and who are not included in any study.

Participation in this study does NOT carry any additional risk to the risks inherent to the operation to which the patient will be subjected. These risks inherent to the operation and which are NOT derived from the study are duly included in the Informed Consent for Surgical Intervention.

The participation of the patients in the study does NOT imply any additional cost (neither for the institution nor for the patient) directly related to the participation in the study. All procedures performed on patients participating in the study are those routinely performed on all patients treated by the shoulder unit in whom a reverse prosthesis has been implanted.

The procedure to be adopted to protect the identity and confidentiality of the data generated by the research complies with the Organic Law on Personal Data Protection (Law 3/2018). All data will be collected confidentially after assignment of a file number, avoiding nominal identification, with health labels and even initials. No patient will be personally identified in any report or publication resulting from this study. The study protocol proposed to you has been drafted in accordance with the Standards of Good with the European Union Standards of Good Clinical Practice and the current revision of the Helsinki Declaration.
